Subjects will be excluded if they had previous brain surgery or other severe neurological problems – intracerebral hemorrhage, traumatic brain injury, central nervous system malignancy, active CNS infection, significant stroke, Alzheimer disease or any type of implanted stimulator including but not limited to Deep Brain Stimulator (DBS) or pacemaker. All subjects must be without evidence of dementia, defined as a score > 24 the Mini-Mental State Examination and able to understand test instructions. Subjects must not have functional blindness (inability to participate in gait and visuomotor assessments) or lower limb amputation higher than the forefoot or any orthopedic problem that precludes performance of physical tests. Subjects must not have known allergy to vitamin B3.

Significant cardiac, pulmonary, hepatic, gastrointestinal, or renal disease (e.g., New York Heart Association Class III or IV congestive heart failure; endocarditis; pulmonary insufficiency symptomatic at rest or with mild physical exertion; acute or chronic hepatitis; renal failure requiring dialysis; second and third degree AV block or sick sinus syndrome), or uncontrolled/advanced diabetes are also exclusionary factors.

Subjects will be excluded if they are taking B3 but will be included if they are taking B complex that has very low dose B3 (25 mg) which has minimal effects on GPR109A (based on our unpublished observation).

Overall, [name] will exercise his clinical judgment to exclude a subject from the study if, in his opinion, he feels that a patient presents with a set of comorbidities which renders them unsuitable for the study.

4. Number of Subjects/Records/Samples Collected

Indicate the total number of subjects to be accrued/records reviewed/samples collected across all sites:
100 No new recruitment.

5. Recruitment Methods

Describe when, where, and how potential subjects will be recruited:

VA clinic (including medical records), word of mouth.

6. Procedures Involved

a. *Describe the procedures involved to include those procedures that are standard evaluation and/or care and those that are solely for research purposes:*

Standard procedures: basic physical examination for strength, speed, coordination, tremor, flexibility, rigidity and reaction time

Research procedures: questionnaire and tests to document health and cognitive status,

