Oxygen consumption rate (OCR) is measured before and after the addition of inhibitors to derive several parameters of mitochondrial respiration. Initially, baseline cellular OCR is measured, from which basal respiration can be derived by subtracting non-mitochondrial respiration. We will study OCR before and after niacin treatment in PD.

b. Describe and explain the study design:

Baseline, 6 month, 12 month and 18 months repeated measures placebo-controlled study

Group 1 – Niacin Arm: 30 PD subjects	Group 2 – Niacinamide Arm: 30 PD subjects	Group 3 – Placebo Wait-listed Arm: 30 PD subjects
Oral 100 mg fixed dose twice daily x 18-months (200 mg total / day) with assessments @ baseline, 6 month, 12 month and 18 months	Oral 100 mg fixed dose twice daily (200 mg total / day) x 18-months with assessments @ baseline, 6 month, 12 month and 18 months	Oral placebo twice daily x 18-months with assessments @ baseline, 6 month, 12 month and 18 months

c. Describe the procedures performed to lessen the probability or magnitude of risks:

Use of slow-release supplement to minimize potential skin itching

d. Describe the duration of an individual subject's participation in the study and the time involved:

18 months supplement study with a baseline, 6 month, 12 month and 18 months each lasting about 1 to 1.5 hr.

7. Data and Specimen Management

a. Describe the data analysis plan, including any statistical procedures:

We will use the Unified Parkinson's Disease Rating Scale (UPDRS) III (Motor Section) as the primary pre- and post-treatment outcome assessment that is recommended for PD studies. Significant changes in outcome measures will be determined by performing a Mixed model analysis of variance, with Groups as the independent factor and Time as the repeated factor.

N/A

b. When applicable, provide a power analysis:

Based on the preliminary data using unpaired simple effects analyses, the minimum number of subjects needed per group to detect a statistical significance @ $p = .05$, 2-tailed and 80% power of detection are as follows:

Outcome measures	Effect size (based on Cohen's d)	# Subjects/group
UPDRS motor	1.46	14
Sleep efficiency (pilot data)	0.97	8

The sample sizes are based on a large effect size, i.e., a grossly observable and clinically meaningful treatment effect. We have demonstrated that this is a reasonable expectation based on the actual effect sizes of the human preliminary data that we have shown. We used simple effects analyses as

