Version Date: 1/4/2019, 7/19/2021,

2/9/2022, 10/26/2022

the basis for the sample size calculations because any sample size calculations based on the full design would require knowledge of the intra-class correlation across the treatments, as well as the carry-over, group, and period effects.

Correlation statistics. Based on the preliminary data's correlation coefficients (r) obtained via simple linear independent correlation tests comparing the variables versus disease severity (UPDRS motor section), the minimum number of subjects needed per group to detect a statistical significance @ $p = .05$, and 80% are as follows:

Outcome measures	r	# Subjects/group
GPR109A levels	0.59	20
Total Sleep Time	-0.57	18
Time to Fall Asleep	0.79	8
Sleep Efficiency	-0.73	10

Based on the simple effects and correlation power analyses above, we propose to collect 30 PD subjects per group (total 90) to account for potential subject dropouts, experimental/data corruption and/or an unexpected increase in the variability of the data. We plan to recruit about 100 subjects to take into account potential drop-outs and an unexpected increase in the variability of the data which impacts the estimated statistical power.

c. *Describe how data and specimens will be handled:*

N/A

i. *What information will be included in that data or associated with the specimens?*

Please refer to 6a above. All data will be coded.

ii. *Where and how data and/or specimens will be stored?*

Specimens: Core lab. Data: Secured computer. ICD will be stored in a locked cabinet. NOTE: All data including specimens will be coded. Specimens will be stored at the VA in room 6B-127, and data will be stored in room 6B-128 (PI's Office).

iii. *How long will the data and/or specimens be stored?*

Indefinitely

iv. *Who will have access to the data or specimens?*

Research team

v. *Who is responsible for receipt or transmission of the data and/or specimens?*

[name] (PI)

vi. *How will data and/or specimens be transported?*

Manually

8. Provisions to Monitor the Data to Ensure the Safety of Subjects

This study involves no more than minimal risk study and this section is not required. **N/A**

The plan might include establishing a data monitoring committee and a plan for reporting data monitoring committee findings to the IRB and the sponsor.

a. *Describe the plan to periodically evaluate the data collected regarding both harms and benefits to determine whether subjects remain safe.*

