c. *If applicable, describe procedures that will be followed when subjects withdraw from the research, including partial withdrawal from procedures with continued data collection.*

A subject who withdraws from the study on their own accord will be replaced by another. A subject who partially withdraws from procedures will remain in the study as long as they continue taking the supplement.

N/A

10. Risks to Subjects

a. *List the reasonably foreseeable risks.*

NA

Low-level temporary discomfort or pain during the blood and lumbar draw. Contraindications for the lumbar puncture: Although there are no absolute contraindications to performing the procedure, caution will be used in patients with the following conditions: 1) Possible raised intracranial pressure; 2) Thrombocytopenia or other bleeding diathesis (including ongoing anticoagulant therapy); 3) Suspected spinal epidural abscess. The side effects associated with lumbar puncture may include following: 1) Discomfort or pain during the procedure; 2) Bleeding into the spinal cord, particularly in people who take blood thinners or have a low platelet count (thrombocytopenia); 3) Temporary headache as a result of CSF leakage; 4) Infection; 5) Nerve damage; 6) Cerebral herniation; 7) Temporary back pain.

We will take a conservative approach in deciding which patient to include from the lumbar procedure. Overall, [name] will exercise his clinical judgment to exclude a subject from the procedure if, in his opinion, he feels that the subject presents with a set of conditions which renders them unsuitable for the procedure.

b. *If applicable, describe any costs that subjects may be responsible for because of participation in the research.*

N/A

Click here to enter text.

c. If applicable, describe risks to others who are not subjects.

N/A

Click here to enter text.

11. Potential Benefits to Subjects

Describe the potential benefits that individual subjects may experience from taking part in the research.

NA

Niacin is an over-the-counter supplement. Our preliminary data indicates that PD patients will benefit from the supplementation. The dosage selected is 100 mg twice daily for 18 months. This dosage is low and do not produce any side effects. If at all, the PD patients will be benefitted by its actions.

12. Confidentiality

Describe the procedures for maintenance of confidentiality.

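### Do the unnamed analysis set and the rule for replacing withdrawn subjects leave the UPDRS III comparison open to completer bias?

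*Combined protocol and SAP*

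**What the plan says.** Section 7a makes UPDRS III the primary outcome and gives the analysis in one sentence, which begins: "Significant changes in outcome measures will be determined by performing a Mixed model analysis of variance, with Groups as the independent factor". Time is the repeated factor, and section 6b sets four visits: baseline and months 6, 12 and 18. Nothing states which subjects enter the model or how missed visits are treated.

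Section 9c is the only text on leavers: "A subject who withdraws from the study on their own accord will be replaced by another", followed by "A subject who partially withdraws from procedures will remain in the study as long as they continue taking the supplement". The entry is marked N/A, as is section 9 as a whole.

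On numbers, section 7b says "we propose to collect 30 PD subjects per group (total 90) to account for potential subject dropouts" and then "We plan to recruit about 100 subjects to take into account potential drop-outs". Section 4 reads "100 No new recruitment". Section 8a reports that recruitment has finished and that the remaining work is analysis of samples already collected.

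On tolerability, section 6c lists "Use of slow-release supplement to minimize potential skin itching", while section 11 says "This dosage is low and do not produce any side effects".

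**The concern.** The term mixed-model ANOVA covers two different practices. Fitted by likelihood, it keeps each subject's available visits. Run as a classical repeated-measures ANOVA on complete cases, it drops everyone who missed a visit. Section 7a does not say which is meant. Section 9c then brings in replacements without saying how they receive an arm or whether leavers are still counted, and it ties continued participation after partial withdrawal to continued supplement use.

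A reader could therefore picture arms refilled to 30 with subjects who finished, and a primary comparison from which leavers have vanished. If subjects doing badly left one arm more often than another, that comparison would show a difference with no treatment effect, and full-looking arms would hide the loss. The choice between the two analyses could also be made after the data are seen.

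**Working it through.** **What the text requires.** Section 7a is satisfied by a likelihood-based model using all visits of all assigned subjects. Section 9c says who continues in the study and that leavers are succeeded by others. It does not say that leavers' earlier visits are discarded, or that subjects who stop the supplement are removed from analysis. A completer analysis is permitted by silence, not prescribed.

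**The plan's own figures.** Section 7b gives 14 per group for d = 1.46 at two-sided 0.05 and 80% power. The usual formula gives 2(1.960 + 0.842)²/1.46² = 7.4, so 8 per group (9 by the t-test). The mismatch is a separate matter and does not affect this point. The step from 90 to 100 equals 90/(1 − 0.10), but no dropout rate is stated. Because 7b says that 30 per group already allows for dropout, 90 cannot be read as a count of completers.

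**Bias in a single completer comparison.** The documents give neither loss by arm nor any link between leaving and outcome, so both are assumed here. Let a fraction q leave each arm, with correlation ρ = 0.3 to 0.5 between leaving and outcome, the same direction in both arms and no true effect:

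bias = ρ × [φ(z_a)/(1 − q_a) − φ(z_b)/(1 − q_b)], where z is the (1 − q) normal quantile.

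- 20% vs 10%: 0.280/0.80 − 0.1755/0.90 = 0.350 − 0.195 = 0.155. Times ρ, this is 0.05 to 0.08 SD.
- 30% vs 10%: 0.348/0.70 − 0.195 = 0.302. Times ρ, this is 0.09 to 0.15 SD.
- Equal loss: 0.

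With 30 assigned per arm and leavers dropped but not replaced, simulation gives nearly the same: 0.045 to 0.077 and 0.090 to 0.146 SD. The bias comes from omitting leavers, not from replacing them.

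**Bias in the planned design.** A simulation of 16,000 runs used three arms, four visits and an assumed between-visit correlation of 0.7. Leaving was weighted 0.3 or 0.5 on the last recorded change from baseline. Completers were refilled to 30 per arm, and the contrast was 18-month change in SD of UPDRS III.

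| Loss by arm | Bias, weight 0.3 / 0.5 | Group × Time rejection |
|---|---|---|
| 20/20/10% | 0.027 / 0.042 | 5.5% / 6.5% |
| 30/30/10% | 0.045 / 0.073 | 6.0% / 8.2% |
| 20% in every arm | 0.000 | 5.7–5.8% |

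The last row is the fair baseline, because the test rejects 5.7–5.8% of the time with no bias at all. Against 5.7%, the excess at 20/20/10% is −0.2 to +0.8 points, and at 30/30/10% it is 0.3 to 2.5 points. If leaving tracks the level of UPDRS III and not its change, the bias is 0.000.

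A second, similar simulation (8,000 runs, Monte Carlo SE about 0.25 points) tested the 18-month contrast itself in completers. Rejection was 5.0/5.4% at 20/20/10% and 5.3/6.3% at 30/30/10%, which is 0.0 to 1.3 points above 5%.

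**Scale.** 0.03/1.46 = 2% and 0.07/1.46 = 5% of the planning effect. This is a rough comparison, since 7b does not say which SD its d uses.

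**What naming the set would gain.** The all-assigned likelihood model had bias of at most 0.002 SD when leaving depended on recorded data. When leaving depended on the unrecorded 18-month change (weight 0.5), it still had 0.058 SD against 0.083 for completers in one loss pattern and 0.099 against 0.141 in another. Both ratios are 0.70.

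**The case for a change.** The best case for a change is that the gap is real, dropout was expected (7b mentions it twice), follow-up is long, and the study is now at analysis, so this is the moment to bind the choice. Neither the N/A marks nor closed recruitment defines who is analysed, and any past replacements are already in the data. One sentence would be cheap. It would also cost little power on the plan's own effect: with 30% off supplement and no effect in them, d falls to 1.46 × 0.7 = 1.02, and 30 per group still gives about 97% power.

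Much of this stands. The plan does not name the set, and a complete-case run is not ruled out. Under extreme loss the bias would matter: if 100 recruited and 90 finished, with all 10 leavers in one arm, the bias would be 0.13 to 0.21 SD and a two-sample comparison would reject 8 to 13% of the time.

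That case needs a reading of 90 that 7b does not support and a split that nothing documents. The only suggested cause of unequal loss is itching, which section 11 contradicts in effect and which nothing connects to motor change. The power figure also works the other way: it gives the analysts no reason to prefer completers.

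**Conclusion.** The analysis set is unstated, but this is missing detail and not a flaw in the design. The sound analysis already fits the wording of 7a, 9c does not instruct otherwise, and the documents show neither a replacement nor unequal, outcome-related loss. Under the stated assumptions, completer bias in the planned three-arm, four-visit design is about 0.03 to 0.07 SD at moderate unequal loss. It is zero with equal loss, or when leaving follows level and not change.

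Those sizes rest on assumed loss rates, an assumed weight of 0.3 to 0.5 on leaving, an assumed between-visit correlation of 0.7 and comparable arms; the documents supply none of these. The judgement would change if the withdrawal records showed heavy loss concentrated in one arm, or if the report used complete cases only. Both would be visible in an ordinary account of withdrawals by arm.

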Blood (2-3 tsp), urine and spinal fluid samples, over-the-counter (non-prescription) vitamin B3 (Niacin or Niacinamide) supplementation.

Blood Collection

Ten ml blood samples will be collected by venipuncture following standard procedures and processed within 4 hours as described earlier ([name] et al., 2014 doi.org/10.1371/journal.pone.0109818). Briefly, purple-top ethylenediaminetetraacetic acid (EDTA) tubes will be used to collect the blood sample and immediately kept in ice. Whole blood will be spun and leukocytes (WBCs) will then be collected and placed in fresh tubes, re-suspended in 4 ml of ACK Lysing Buffer (Lonza cat # 10-548E) and be incubated for 10 min at room temperature before being spun again at 300 ×g for 5 min. The process will be repeated one more time. Supernatant will be discarded from the clean WBCs pellet. WBCs pellets will be washed twice with 1 ml of PBS and WBCs pellets will then be stored at -80 °C until further analyses ([name] et al., 2014).

Analytical flow cytometry

As described previously (Stranahan et al., 2016), whole blood cells will be incubated with antibodies for surface markers including CD11b, CD68, F4/80 (M1), CD206 (M2), and GPR109a. Next, cells will be fixed and permeabilized using fix/perm concentrate (eBioScience) before incubation with antibodies for intracellular staining of IL-10 (functional M2 s). Cells will then be washed and run through a four-color flow cytometer (FACS Calibur). Data will be collected using Cell Quest software. Samples will be double-stained with control IgG (isotypes) and cell markers to assess any spillover signal of fluorochromes. Gating will exclude dead cells and debris using forward and side scatter plots.

Western Blot

WBCs will be separated as described previously ([name] et. al 2014). WBCs will be subjected to lysis by RIPA buffer with a protease inhibitor cocktail and protein concentration will be measured by Bradford reagent (Bio-Rad). Again the samples will be subjected to western blot using Bio-Rad 4–15% SDS-PAGE then transferred to PVDF membrane followed by incubation with respective antibody overnight and developed with an ECL kit (Giri et al., 2007).

Saehorse

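### Section 9c ties staying in the study to continued use of the supplement, and nothing provides follow-up after stopping, so 18-month outcomes risk being selectively missing

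*Combined protocol and SAP*

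**What the plan says.** The prompt of Section 9c asks what happens when subjects withdraw, "including partial withdrawal from procedures with continued data collection". The answer has two sentences. The first covers full withdrawal: "A subject who withdraws from the study on their own accord will be replaced by another". The second covers partial withdrawal: "A subject who partially withdraws from procedures will remain in the study as long as they continue taking the supplement".

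Four other places bear on this:

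- **Section 6a** lists "over-the-counter (non-prescription) vitamin B3 (Niacin or Niacinamide) supplementation" among the research procedures.
- **Section 6b** describes a "Baseline, 6 month, 12 month and 18 months repeated measures placebo-controlled study".
- **Section 6c** gives one risk-reducing measure: "Use of slow-release supplement to minimize potential skin itching".
- **Section 7a** takes UPDRS III "as the primary pre- and post-treatment outcome assessment that is recommended for PD studies". The analysis is given as: "Significant changes in outcome measures will be determined by performing a Mixed model analysis of variance, with Groups as the independent factor", with Time as the repeated factor. It names no analysis set, no estimand and no rule for missing outcomes.

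On status, Section 4 says there is no new recruitment. Section 8a says recruitment is complete and only collected samples remain to be analysed. Section 9 is marked N/A, and a further N/A follows the 9c text.

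**The concern.** The rule makes retention depend on adherence. A subject who refuses blood or lumbar puncture but keeps taking the product stays in. A subject who stops the product but would come back for a motor examination does not meet the condition for staying. If that subject stopped before the first follow-up visit, only a baseline UPDRS III would exist.

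This is a matter of what is collected, and it comes before any choice of analysis set: no analysis set can include an outcome that was not measured. Subjects who stop over 18 months may do so because of a reaction or because they feel no benefit, and either reason may be related to the outcome. The 18-month comparison would then lean towards subjects who tolerated the product and felt well on it. A mixed model would have to assume that the unobserved course of stoppers can be predicted from what was observed before they stopped.

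**Working it through.** **1. Does any passage provide follow-up after stopping?**

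| Place | What it contributes |
|---|---|
| 6a | The supplement is a research procedure, so stopping it can be read as partial withdrawal |
| 6b, 6d, 8d | Visits at baseline, 6, 12 and 18 months; silent on subjects who have stopped |
| 7a | Model named; silent on missing outcomes |
| 9a, 9b | Not filled in, marked N/A |
| 9c, first sentence | Full withdrawal leads to replacement |
| 9c, second sentence | Partial withdrawal: retained on condition that the product is still taken |

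The only rule on partial withdrawal is the conditional one, and no passage offers a visit after stopping. For the placebo arm, 'the supplement' is undefined; the natural reading is the assigned product.

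**2. Size of the possible bias.** Let m be the fraction of an arm that stops. Let D be the number of points by which the stoppers' true 18-month UPDRS III change is worse than the continuers'.

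- Mean change of the whole arm = (1 − m) × C + m × (C + D) = C + m × D, where C is the continuers' mean change.
- A continuers-only mean is therefore too favourable by m × D.
- For active (1) against placebo (0), the comparison favours active by **m1 × D1 − m0 × D0**.

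The documents give neither m nor D, so every value below is an assumption.

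| m1 | m0 | D1 | D0 | Bias in favour of active (points) |
|---|---|---|---|---|
| 0.20 | 0.10 | 5 | 5 | 1.0 − 0.5 = 0.5 |
| 0.30 | 0.10 | 10 | 10 | 3.0 − 1.0 = 2.0 |
| 0.20 | 0.20 | 5 | 5 | 1.0 − 1.0 = 0 |
| 0.20 | 0.20 | 5 | 10 | 1.0 − 2.0 = −1.0 |

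The last two rows show that equal stopping removes the bias only if D is also equal, and that the bias can run either way.

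The formula is for a continuers-only comparison. A likelihood-based mixed model that keeps the 6- or 12-month visits of later stoppers may do better. It has little to work with for a subject who stopped before month 6.

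**3. Is power at stake?** The plan's figure for UPDRS motor is 14 per group at d = 1.46, two-tailed 0.05 and 80% power. It does not reproduce: 2 × (1.960 + 0.842)² / 1.46² = 7.4, so 8 per group, or 9 with the t distribution. That mismatch is a separate matter. What counts here is power at d = 1.46 by a two-sided t-test:

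- 30 per group: above 99.9%.
- 18 per group (40% lost and nobody replaced): 98.9%.

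Lost numbers do not threaten the plan at its own effect size.

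**The case against.** The strongest objection is that 9c does not say stoppers are removed or their visits cancelled. Section 9a lists no circumstances for withdrawing a subject without consent, and dropping a willing stopper would be one. Section 8d sets the visits with no adherence condition. The sentence in 9c also fits best a subject who declines tests while still on product. A reader might infer that later outcomes of stoppers were in fact never collected. The documents do not establish that; it is a consequence of the 'as long as' condition, not a recorded fact. What stands is that this condition is the only stated rule and nothing offsets it.

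Three further points have force:

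- **Numbers.** A reader might infer that 20% stopping cuts each arm from 30 to 24 and widens intervals accordingly. The documents do not support this, because withdrawn subjects are replaced and about 100 are recruited to allow for drop-outs. Replacement restores the headcount, not the outcomes of the subject who left.
- **Imbalance.** A reader might infer that stopping must differ by arm. Section 6c foresees possible itching, but Section 11 says the dosage has no side effects, and lack of benefit can arise in any arm. Imbalance is plausible, not shown.
- **Status.** With recruitment closed and Section 9 marked N/A, rewording 9c cannot recover missed visits. This limits the remedy. It does not remove the defect, since 9c remains the only account of how outcomes were handled after stopping.

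**Conclusion.** The point holds as a risk created by a stated rule. Section 9c, read naturally, does not retain a subject who stops the assigned product, and no other section provides for that subject's later UPDRS III or samples. The comparison at 18 months is exposed to selective missing outcomes, and it drifts towards an effect in those still taking the product without the plan saying that this is the target.

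The size cannot be derived from the documents. The range of 0.5 to 2.0 points rests on assumed stopping of 20% to 30% against 10%, a D of 5 to 10 points common to both arms, and a continuers-only comparison. With other values the bias can be nil or reversed, and a mixed model may reduce it. Loss of power at d = 1.46 is not part of the case. The change should be made: it is cheap, and the harm cannot be repaired once visits are missed.

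**What to change.** **For any remaining follow-up or a successor protocol**, replace the second sentence of 9c with wording such as: *Anyone who stops the assigned product (active or placebo) or declines a procedure stays in the assigned group and is invited to all remaining assessments, unless consent for follow-up is withdrawn. The stop date and reason are recorded.* This concerns data collection only and says nothing about when a subject should stop.

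**For the data in hand**, add to Section 7a:

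1. A table by arm of who stopped, when and why, and who was replaced, as far as the records allow.
2. A statement that every collected outcome is analysed in the assigned group, including any obtained after stopping and those of subjects later replaced.
3. A sensitivity analysis to the mixed model, for example delta-adjusted: impute the missing post-stopping UPDRS III scores, make them worse by a range of values (such as 0 to 10 points) set separately for each arm, and report where the conclusion changes.

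**Cost.** For future follow-up: a wording change, plus visits of 1 to 1.5 hours (Section 6d) and the visit voucher (Section 13). For the present data: a little more analysis work. Visits made off product may dilute the estimated effect; the stop dates let that be shown.
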